Sample Size. The primary analysis of this study is to compare the quit rates between groups. The sample size estimation is based on the results from Oncken et al.⁶ the quit rates at 12 weeks for 0.5, 1.0 mg b.i.d. titrated groups and control group are approximately 45%, 60% and 15%. In an OTC setting, we assume the rates would reduce by half. Therefore, 23%, 30% and 8% are used to determine the sample size. Since we are interested in comparing the two active treatment arms with the control arm, to control for the overall type I error rate, the Bonferroni adjustment is applied: for each comparison, the type I error is 0.025. With 110 participants per group, we have at least 80% power to detect a difference of 23% vs. 8% (0.5mg vs. control) by the chi-square test. Even though a smaller sample size is required to detect a difference of 30% vs. 8% (1.0mg b.i.d. vs. control), we plan to enroll equal number of participants for each arm.

For the EMA component of the study, we anticipate the primary outcomes for each treatment condition in the EMA subgroup will not be statistically different from the non-EMA sample and plan to analyze the primary outcomes based on the combined sample. However, the data collected will provide information to quantify the longitudinal within subject association. In particular, we hypothesize that the severity of side effect will increase in the first 5 days after the initiation of treatment, and expect the odds of side effect at day 5 is three times the odds at day 1. Based on our simulations (type I error 0.05, 5 time points, and intra-class correlation 0.3), with 25 participants per group, we have at least 80% power to detect an odds ratio of 3.

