Data Sharing Plan. The information that we will collect includes medically-related information that is protected and must remain confidential, so all standard methods to protect participant confidentiality will be employed, including maintaining information in password protected encrypted databases to reduce the risk of a data breach. Shared data across the two study sites will likewise be password protected and encrypted. After study completion, any outside requests for data will require a data sharing agreement that assures the following: (1) all data must be maintained in a secure fashion using appropriate technology, (2) commitment to use the data only for the research purposes requested, and (3) all shared data must either be destroyed or returned, including written assurances to that effect.

Statistical Analysis Plan

Main study. The participation flow will be reported following CONSORT guidelines. Intention to treat analysis will be applied for all statistical analyses. The data collected from the study will be summarized by the descriptive statistics for overall and by treatment condiction (1mg b.i.d., .5mg b.i.d. and placebo) and by the application of EMA (yes/no). The primary analysis will include estimating and comparing the guit rates between treatment arms. We will fit a logistic regression to model the probability of smoking cessation at 12 weeks with treatment condition, application of EMA and the interaction term of the two main effects as independent variables. If the interaction term is not significant, this implies the guit rates for the same treatment condition are similar in those with and without the utilization of EMA, and we will drop the interaction term and fit a model with main effects only. The comparison will be perfromed by the Wald test from the logistic regression with Bonferroni adjustment to account for multiple comparisons. The point estimate of guit rate and 95% confidence interval (CI) for each treatment condition will be reported. If the interaction term is significant, we will conduct the comparisons in EMA and non-EMA subgroups. A similar approach will be applied to the analysis of adherence and adverse events. These two outcome variables can be analyzed as a dichotomous (yes/no) or count variable (pill count and number of adverse events), and the logistic regression and Poisson regression will be used to evaluate whether group differences occur. In the secondary analysis, to evaluate

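### Plain Bonferroni on the two active-versus-placebo tests is valid, but Holm's step-down keeps the same nominal familywise error and adds about 4 to 7 points of power for 0.5 mg on the plan's rates

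*Combined protocol and SAP*

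**What the plan says.** Section E, Sample Size, defines the confirmatory comparisons: "Since we are interested in comparing the two active treatment arms with the control arm". It then fixes the multiplicity rule: "to control for the overall type I error rate, the Bonferroni adjustment is applied: for each comparison, the type I error is 0.025". On the assumed rates, "23%, 30% and 8% are used to determine the sample size" (0.5 mg, 1 mg and placebo in that order). It gives 110 participants per group for at least 80% power on 0.5 mg versus placebo by the chi-square test, and notes that 1 mg versus placebo needs fewer.

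Section E, Statistical Analysis Plan, Main study, repeats the method for the primary model: "The comparison will be perfromed by the Wald test from the logistic regression with Bonferroni adjustment to account for multiple comparisons". It does not say how many comparisons are counted. The only interval it promises is a 95% confidence interval for each arm's quit rate.

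Section C, Study Design, plans a total of 432, which at 1:1:1 is 144 per arm. Primary Objective 2 and Hypothesis 2 in Section B also compare 0.5 mg with 1 mg. No step-down, hierarchical or other sequential rule appears in the documents.

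**The concern.** Bonferroni holds each test at 0.025 whatever the other test shows. On the plan's rates the 1 mg test is very likely to pass. When it does, only one hypothesis remains and it could be tested at 0.05 without exceeding the overall 5%. Bonferroni leaves that alpha unused on 0.5 mg versus placebo, which is the comparison that sets the sample size and carries the claim for the lower dose.

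At stake is a 0.5 mg p-value between 0.025 and 0.05 when 1 mg has clearly beaten placebo. Bonferroni does not declare 0.5 mg effective in that case. Holm does, under the same nominal familywise guarantee.

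**Working it through.** **Inputs.** Sample Size section: rates 8% (placebo), 23% (0.5 mg) and 30% (1 mg); alpha 0.025 per test; 110 per group; chi-square test. Study Design: 432 in total, so 144 per arm. Assumed: two-sided tests, because sidedness is not stated and the two-sided version reproduces the plan's figure; and one pooled analysis.

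**1. Reproduce the plan's figure.** For 23% versus 8%, the mean rate is 0.155. The pooled term is √(2 × 0.155 × 0.845) = 0.5118 and the unpooled term is √(0.23 × 0.77 + 0.08 × 0.92) = 0.5007.

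n = (2.2414 × 0.5118 + 0.8416 × 0.5007)² / 0.15² = 1.5686² / 0.0225 = 109.4, so 110. Power at 110 is Φ[(0.15 × √110 − 2.2414 × 0.5118) / 0.5007] = Φ(0.851) = 80.3%. The stated figure is right.

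**2. Upper bound on the gain.** If the 1 mg test always passed, Holm would test 0.5 mg at 0.05 (z = 1.960) instead of 0.025.
- 110 per arm: Φ(1.139) = 87.3% against 80.3%, a gain of 7.0 points.
- 144 per arm: Φ(1.592) = 94.4% against 90.4%, a gain of 4.0 points.

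**3. Allow for the 1 mg test sometimes failing.** The two tests share the placebo arm, so condition on the placebo count c, which has binomial weight w(c). Let L(a) and H(a) be the probabilities, given c, that the 0.5 mg and 1 mg tests reach level a.
- Bonferroni power for 0.5 mg: Σ w(c) · L(0.025).
- Holm power for 0.5 mg: Σ w(c) · [L(0.025) + (L(0.05) − L(0.025)) · H(0.025)].

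The added term cannot be negative, so Holm never loses power. Summing over the binomial distributions gives the figures below, which agree with simulated trials to about 0.1 point. The Wald test here is the log odds ratio without the EMA term. Gains are taken before rounding.

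| Per arm | Test | Bonferroni | Holm | Gain (points) |
|---|---|---|---|---|
| 110 | chi-square | 81.7% | 88.5% | 6.9 |
| 110 | Wald | 80.9% | 87.5% | 6.6 |
| 144 | chi-square | 91.5% | 95.2% | 3.8 |
| 144 | Wald | 91.0% | 94.8% | 3.8 |

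On these rates the 1 mg test passes 0.025 (chi-square) in 98.2% of trials at 110 per arm and 99.7% at 144, which is why the gain lies close to the bound.

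**4. Vary the 1 mg rate,** keeping 0.5 mg at 23% and placebo at 8% (chi-square).

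| 1 mg rate | Gain at 110 (points) | Gain at 144 (points) |
|---|---|---|
| 30% (plan) | 6.9 | 3.8 |
| 23% | 4.8 | 2.9 |
| 20% | 3.0 | 1.9 |
| 15% | 0.6 | 0.4 |

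**5. False claims.** With all arms at 8% and 110 per arm, the chance of at least one rejection (chi-square) is 4.6% under both methods, because they make a first rejection in exactly the same trials. With 0.5 mg at 8% and 1 mg at 30%, the chance of a false 0.5 mg claim changes as follows.
- 110, chi-square: 2.5% to 5.2%.
- 110, Wald: 1.4% to 4.0%.
- 144, chi-square: 2.4% to 4.7%.

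The 5.2% comes from the discreteness of the chi-square test at nominal 0.05, not from Holm.

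**The case against.** The plan contains no error here. It names a family, a valid method and an alpha, and its sample size is correct. At the planned 144 per arm Bonferroni already gives about 91% power for 0.5 mg, so the practical gain is under 4 points. The gain also leans on an assumed 30% for 1 mg, while Hypothesis 2 expects the two doses to be comparable. With both at 23% and 144 per arm it is 2.9 points. All of this stands, and it limits the point to an efficiency improvement.

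A reader might infer that Holm costs nothing. It does cost something. When 1 mg works, the chance of a false 0.5 mg claim roughly doubles, though it stays at about the nominal 5%. Simultaneous intervals that match Holm are also less simple than Bonferroni intervals. The plan promises none for the differences between arms, so no stated output is lost. The COVID-19 text under Recruitment shows a study already under way, so relaxing a threshold is defensible only before unblinding.

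A reader might also infer that the Statistical Analysis Plan spreads Bonferroni over all three pairs, which would cut normal-approximation power at 110 per arm to 75.6% and break the promised 80%. The documents do not support this: the Sample Size section counts only the two tests against placebo, and the later sentence gives no number. Even with three pairs, power at 144 per arm would be 87.5%.

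Finally, the calculations pool the in-person and remote cohorts, whereas the plan analyses them separately first and only might combine them. No split is given. At an assumed 72 per arm the gain would be larger, about 10 to 11 points.

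**Conclusion.** The point holds as an improvement to a valid plan. It does not show that the trial is underpowered or that Bonferroni is wrong, and neither inference would be supported by the documents. Holm has the same nominal familywise control and rejects everything that Bonferroni rejects. On the plan's rates it adds about 7 points of power for 0.5 mg at 110 per arm and about 3.8 points at 144.

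These sizes assume two-sided tests, a pooled analysis, no EMA term in the model, and a 1 mg rate of 30%. The gain shrinks towards zero as the 1 mg effect weakens, and it is never negative. Nominal 5% control belongs to Holm as a procedure. With the chi-square approximation at 110 per arm, the error on a null 0.5 mg arm can slightly exceed 5%, whereas with the Wald test that the plan specifies it was 4.0% in the same scenario.

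**What to change.** Before unblinding, amend the Sample Size section and the Main study paragraph of the Statistical Analysis Plan to state that:

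- the confirmatory family is the two active-versus-placebo comparisons;
- they are tested with the planned Wald tests by Holm's procedure at a familywise two-sided 0.05, the smaller p-value at 0.025 and, if it passes, the other at 0.05;
- the 0.5 mg versus 1 mg comparison in Primary Objective 2 is outside this family and is reported as an estimate with a confidence interval. The trial is not sized for it: power for 30% versus 23% at two-sided 0.05 is about 22% at 110 per arm and 27% at 144.

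Keep the stated sample size, whose power then becomes a conservative figure.

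The cost is a short text amendment, with no added participants, visits or data. The trade-offs to accept are the higher chance of a false 0.5 mg claim when 1 mg works, and more complex simultaneous intervals should they be wanted later.

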A time will be scheduled for a phone call or Zoom meeting, the study will be described in written format and orally by study staff, and participants will be asked to electronically sign the consent form. The following will occur during Screening/Baseline:

- Informed Consent (electronic)
- Subject Demographics (see Appendix 1)
- Smoking, tobacco, and cessation medication use history (see Appendix 2)
- Rapid Estimate of Adult Literacy in Medicine (REALM, see Appendix 3)
- Minnesota Nicotine Withdrawal Scale (MNWS, see Appendix 4). This brief staff or subject administered form will assess cigarette-related craving and withdrawal.
- Medical History—Pertinent medical history will be assessed and documented on the Medical History CRF by the study coordinator through a review of systems, allergies, and recent surgeries
- Previous and Concomitant Medications. Medications taken within the previous 30 days of the Screening/Baseline visit will be documented in the Concomitant Medication CRF
- Fagerström Test of Cigarette Dependence (FTCD, see Appendix 7). This 5 item subject completed questionnaire measures dependence on cigarettes.

- If the subject requires study approval from their own physician, the Investigational Product will be dispensed upon receipt of the signed authorization (Appendix 8)
- Suicidal Behavior Questionnaire (Appendix 15)

Screening/Baseline for the Remote Cohort – Visit 2

- Urine pregnancy test for all females. This will be mailed to the participant after they have completed Screening/Baseline Visit 1.
 - Urine cotinine test. This will be mailed to the participant after they have completed Screening/Baseline Visit 1.
 - If subject meets all inclusion and exclusion criterion, a study ID will be assigned and he/she will be randomized in a 1:1:1 fashion to 1.0 mg b.i.d. varenicline, .5mg b.i.d. varenicline, or placebo. Participants and study staff will be blinded to the assignment.
 - Investigational Product educational information will be provided to participants
 - The Investigational Product will be dispensed to be used for the full 12 weeks of treatment
- Participants will have 30 days from the start of their first screening visit to complete all the procedures and begin the medication
- Participants will be asked to contact study staff when they receive the study medication to inform staff when they will be starting the medication so they remaining visits can be based on the medication start date.

Week 2 Visit for the Remote Cohort

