Adverse Event (AE) Definitions. Any negative event subsequent to signing consent but prior to the week 13 visit will be considered a potential adverse event to be addressed and followed, regardless of whether it is related to use of study medication. Examples of AEs include: (1) Clinical signs and symptoms, (2) Abnormal test results, (3) Worsening of existing medical conditions. The licensed medical professional (LMP) will consider adverse events serious if the event: (1) is life threatening, (2) results in death, (3) leads to incapacity, hospitalization, or serious impairment of normal life, (4) congenital abnormality or birth defect. Serious AEs will be reported to the IRB within 24 hours of the site becoming aware of the event. Once an adverse or serious adverse event is identified, it must be followed and recorded, such that subsequent to the designation each event

outcome should be characterized as follows: 1 = Still present, 2 = Resolved with Sequelae, 3 = Resolved without Sequelae, 4 = Lost to follow-up/Unknown, 5 = Death.

Determination of Severity. The study coordinators will make a determination of AE severity and provide a grade for each event according to the following criterion: Mild: Symptoms cause little discomfort, are easily tolerated, and do not significantly interfere with normal everyday activities. Moderate: Symptoms are uncomfortable and interfere with normal everyday activities. Severe: Symptoms cause significant impairment of everyday activities, incapacitation, or death

Determination of Causality. The LMP will make a determination the causality of each adverse event in relation to the study medication using the following criteria: 1 = Definite, 2 = Probable, 3 = Possible, 4 = Remote, 5 = Definitely Not

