participants no more than 90 seconds to complete. To reduce missing data, participants who miss more than two sequential days of evening daily diaries or complete fewer than three scheduled prompts a day for two sequential days will receive encouragement texts and calls from an RA to troubleshoot any problems with the app and encourage compliance.

Definitions of Success

FDA Abstinence Criteria. As indicated earlier, in all studies that assess medications for smoking cessation, the FDA typically requires verification of 28 days of continuous abstinence, i.e.; not a single puff from a single cigarette. The FDA does not require the 'clock' to start at a consistent time point after study enrollment. Thus, in many studies the 'clock' on that 28 days begins two weeks after study medication has begun, while in other studies the 'clock' starts at a different time point. In the current study, we will follow the protocol used in the varenicline pivotal trials. ^{6,17-20} The primary study outcome in the proposed study will be continuous abstinence between weeks 8 and 12 after study medication has begun. Subjects who are randomized but who never obtain medication will be considered treatment failures and will be included in the denominator in the intent-to-treat analyses.

D. DATA SAFETY MONITORING PLAN

Participant Safety. This study includes the use of a medication, varenicline, that is FDA-approved, as well as the same medication at a lower dose than approved by the FDA, in order to assess whether smokers can choose and use the medication without a healthcare provider prescription. Given the existing data, the likelihood of participants experiencing a serious adverse event from the use of varenicline is very low. In fact, in one of the largest smoking cessation studies ever conducted, the adverse events related to varenicline were similar to those from the nicotine patch, which is already approved as an OTC medication.

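### Intention-to-treat for every analysis, with adverse events defined from consent, can let undosed people and pre-dose events pull the safety ratios towards 1, mainly in the remote cohort

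*Combined protocol and SAP*

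**What the plan says.** - **Analysis set.** Section E, Statistical Analysis Plan (Main study): "Intention to treat analysis will be applied for all statistical analyses". After describing the quit-rate model it adds: "A similar approach will be applied to the analysis of adherence and adverse events". These outcomes may be yes/no or counts, and "the logistic regression and Poisson regression will be used to evaluate whether group differences occur". The text names no safety set, treatment-emergent rule or exposure offset.
- **Event window.** Section C, Adverse Event (AE) Definitions: "Any negative event subsequent to signing consent but prior to the week 13 visit will be considered a potential adverse event". This applies "regardless of whether it is related to use of study medication". A licensed professional rates causality, but no analysis uses the rating.
- **Time from consent to first dose.** Remote participants consent at Visit 1, are randomised at Visit 2 and then receive the product by mail. The Visit 2 procedures say: "Participants will have 30 days from the start of their first screening visit to complete all the procedures and begin the medication". In-person participants normally consent, are randomised and receive product at one visit; dispensing is later if their own physician must first approve.
- **Randomised but undosed.** Definitions of Success: "Subjects who are randomized but who never obtain medication will be considered treatment failures". They stay in the intention-to-treat denominator. That sentence concerns the quit outcome, but it shows that such people are expected.
- **Objectives.** Both primary objectives name safety alongside efficacy. Hypothesis 3 predicts a dose response in side effects.

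**The concern.** For quit rates, keeping undosed people as failures is the cautious choice. For adverse events the same rule works the other way. A person who takes no drug cannot have a drug-caused event, and neither can anyone before the first dose. If both occur equally in all arms, as blinding and randomisation suggest, they create no false difference but shrink a true one.

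The shrinkage makes it easier to conclude that varenicline is safe without support, and harder to detect the dose response in Hypothesis 3. The amount is also likely to differ between cohorts. The plan analyses the cohorts separately and may combine them if the outcomes look similar, so unequal dilution could affect that judgement too.

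**Working it through.** The documents give no figure for the safety comparison. Their sample size (110 per group for 23% vs 8%, at least 80% power, type I error 0.025) reproduces: 110 per group and 80.3% power with a two-sided test, pooled variance and no continuity correction. It is an efficacy figure and this point does not touch it.

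**Inputs from the documents.** Pre-dose time: at most 30 days (remote). Week 13 target: day 105 (Table 2, used for both cohorts; remote visits are timed from medication start). Total 432 at 1:1:1, so 432/3 = 144 per arm.

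**Assumptions.** Event rates, the share of non-starters and the typical pre-dose gap are not given. Steps 1 and 2 assume a constant background rate, full capture of pre-dose events, and a true ratio that applies from first dose to week 13.

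**Step 1: pre-dose events, counts.** Observed ratio = (pre + 105 × RR) / (pre + 105).
- RR 2.0, 7 days: (7 + 210)/112 = 1.94.
- RR 2.0, 30 days: (30 + 210)/135 = 1.78.
- RR 3.0, 30 days: (30 + 315)/135 = 2.56.

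If week 13 is taken as 13 × 7 = 91 days, the first two become (7 + 182)/98 = 1.93 and (30 + 182)/121 = 1.75.

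**Step 2: non-starters, counts.** Assume 10% in each arm and 30 pre-dose days.
- If they report background events throughout: (30 + 105 × (0.9 × 2 + 0.1))/135 = 229.5/135 = 1.70.
- If they report no events, both arms' counts are multiplied by 0.9 and the ratio stays at 1.78.

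**Step 3: yes/no outcome.** Let f be the non-starter share, carrying the placebo risk, and q the chance of an independent pre-dose event, both equal across arms. Then the placebo risk is 1 − (1 − p0)(1 − q), the active risk is 1 − (1 − [f·p0 + (1 − f)·p1])(1 − q), and the risk difference is (1 − f)(1 − q)(p1 − p0). With assumed true risks of 10% and 20%:

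| f | q | Risks compared | Risk difference kept | Odds ratio |
|---|---|---|---|---|
| 0 | 0 | 10.0% vs 20.0% | 100% | 2.25 |
| 5% | 2% | 11.8% vs 21.1% | 93% | 2.00 |
| 10% | 5% | 14.5% vs 23.1% | 85.5% | 1.77 |
| 20% | 10% | 19.0% vs 26.2% | 72% | 1.51 |

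If non-starters report no events (f = 10%, q = 0), the risks are 9% and 18%. The risk ratio stays 2.0, the odds ratio falls only to 2.22, and the difference falls from 10 to 9 points.

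**Step 4: power for the same risks.** With 144 per arm and two-sided 0.025, power is 55% undiluted, and 46%, 35% and 22% for the three diluted rows. A fair comparison must also drop the non-starters: at f = 10%, about 130 dosed per arm (144 × 0.9) give about 50%, against 35% for the third row. These figures pool the cohorts; separate analyses would have less power.

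**The case against.** The strongest reply is that the adverse event definition is a rule for recording and following events. The analysis plan does not say which recorded events enter the models. That is so: the text does not state that pre-dose events are analysed. But it contains no rule that leaves them out, and it sets intention-to-treat for every analysis.

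Several limits on the size also stand:
- Tables 1 and 3 (the visit schedules) first mark adverse events at week 2, and remote visits run from medication start, so many pre-dose events may never be recorded.
- Thirty days is a remote-only maximum, and part of it falls before randomisation.
- Withdrawal symptoms after the advised quit date, day 8 of medication or later, would raise the background rate after dosing, which weakens the dilution.
- Non-starters may have no follow-up timed from a start date, and if they report nothing, rate ratios do not move.
- Part of the plan is already tied to treatment: the trend models run from its initiation, and the EMA side-effect data cover the first two weeks of use.

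A reader might infer that the whole trial's safety comparison is heavily diluted. The documents do not support that, for the reasons above and because in-person drug is usually dispensed at baseline. Nor does the treatment-failure sentence set safety denominators; only the blanket intention-to-treat statement reaches that far.

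**Conclusion.** The point holds as a matter of method. Followed as written, the plan allows undosed people and pre-dose events into the adverse event comparison, and the direction is towards no difference. This attenuation favours a finding of safety and works against Hypothesis 3; it is not a bias towards everything the investigators hope to show.

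The size cannot be fixed from the documents. It is probably small in the in-person cohort and larger in the remote cohort. On the assumptions of step 1, a true rate ratio of 2.0 would appear as between about 1.94 and 1.78, the lower value being the 30-day extreme. Non-starters shrink odds ratios and risk differences, but shrink rate ratios only if they report background events. The change is worth making because safety is in both primary objectives and the better method is standard.

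**What to change.** Limit intention-to-treat to efficacy. For adverse events, pre-specify:
- a safety set of participants who took at least one dose, as the main analysis;
- events that start or worsen on or after the first dose;
- person-time from first dose as the Poisson offset;
- a separate listing of pre-dose events, with collection from consent unchanged;
- the intention-to-treat version as a sensitivity analysis.

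Confirm that two dates are captured. Remote participants tell staff when they will start, which is an intended date; no first-dose date is described for the in-person cohort. The adverse event text lists severity, causality and outcome, but not onset date. If these dates are already on the case report forms, the cost is plan wording. If not, a field or two must be added, and for people already enrolled the dates would have to be recovered where possible. One small downside is that the safety set is not strictly the randomised set, which is why the sensitivity analysis should stay.

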- Minnesota Nicotine Withdrawal Scale (MNWS, see Appendix 4). This brief staff or subject administered form will assess cigarette-related craving and withdrawal.
- Medical History—Pertinent medical history will be assessed and documented on the Medical History CRF by the study coordinator through a review of systems, allergies, and recent surgeries
- Previous and Concomitant Medications. Medications taken within the previous 30 days of the Screening/Baseline visit will be documented in the Concomitant Medication CRF
- Body weight and height-height in meters (to the nearest cm) and weight in kilograms (to the nearest 0.1 kg in light indoor clothing and without shoes will be measured.
- Vital signs including blood pressure and heart rate, measured after the subject has been seated and resting for at least 5 minutes.
- Fagerström Test of Cigarette Dependence (FTCD, see Appendix 7). This 5 item subject completed questionnaire measures dependence on cigarettes.
- Urine pregnancy test for all females
- Urine drug screen. The urine test for drugs of abuse (eg opiates, amphetamines, benzodiazepines, cocaine or other substances) will be performed only at the Screening/Baseline Visit. Subjects who test positive will be excluded, unless they can provide the clinic with a copy of a current prescription for opioids or stimulants.
- A portion of this urine will be stored for exploratory analysis of nicotine and nicotine metabolism that might be related to treatment outcomes, only at the ASU site.
- Breath Carbon Monoxide test. The breath CO will be collected after a 15 second breath hold using the Bedfont Micro Plus (Bedfont Inc).

- If the subject requires study approval from their own physician, the Investigational Product will be dispensed upon their return to the clinic with the signed authorization (Appendix 8)
- If subject meets all inclusion and exclusion criterion, a study ID will be assigned and he/she will be randomized in a 1:1:1 fashion to 1.0 mg b.i.d. varenicline, .5mg b.i.d. varenicline, or placebo. Participants and study staff will be blinded to the assignment.
- Investigational Product educational information will be provided to participants
- The first five weeks of Investigational Product dispensed
- If randomized into the substudy, subjects will be instructed on how to respond to the text messages
- Suicidal Behavior Questionnaire (Appendix 15)

Week 2 Visit for the In-person Cohort

- Telephone call
- Minnesota Nicotine Withdrawal Scale

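### The primary logistic model adjusts only for randomised EMA assignment and leaves out baseline dependence measures already collected, a small missed gain in efficiency rather than an error

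*Combined protocol and SAP*

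**What the plan says.** Section E, Statistical Analysis Plan, Main study, fits a logistic regression for cessation at 12 weeks "with treatment condition, application of EMA and the interaction term of the two main effects as independent variables". If the interaction is not significant, "we will drop the interaction term and fit a model with main effects only". Then: "The comparison will be perfromed by the Wald test from the logistic regression with Bonferroni adjustment to account for multiple comparisons". A quit rate with a 95% CI is promised for each arm. No baseline characteristic, site or cohort is in this model.

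Participant characteristics appear in the secondary multivariable models and in the first Secondary Objective, as moderators. Site appears only in an exploratory three-level mixed model. Under Analysis of the Remote Cohort, the two cohorts are analysed separately and may be combined if their results look similar.

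On EMA, the sub-study Methods assign 25 people per condition at random, and the Sample Size paragraph anticipates no difference in primary outcome between EMA and non-EMA participants.

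The baseline procedures for both cohorts include the FTCD, described with the words "This 5 item subject completed questionnaire measures dependence on cigarettes", and the Appendix 2 history form, which asks for average cigarettes per day. Both come before randomisation. The Study Design section describes block randomisation and names no stratification factor.

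**The concern.** The one adjustment term in the primary model is a factor that the plan expects to explain nothing, while variables that might explain part of the outcome are collected and left out. If dependence or consumption predicts quitting, including it would sharpen the treatment comparison and allow for chance imbalance between arms, which no named stratification factor controls. Expected placebo quitters are few, so an imbalance in dependence could move the estimate noticeably. Naming the covariate in advance would also remove any later choice about what to adjust for. The secondary covariate models do none of this for the primary test.

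**Working it through.** **Inputs from the documents.** Quit rates: "23%, 30% and 8% are used to determine the sample size" (0.5 mg, 1.0 mg, placebo). Alpha: "for each comparison, the type I error is 0.025", taken as two-sided because sidedness is not stated. The Sample Size paragraph claims at least 80% power at 110 per arm for 23% vs 8% by chi-square test. Total N is 432 allocated 1:1:1, so 432 / 3 = 144 per arm. EMA: 25 per arm.

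**Assumptions.** The baseline covariate is standard normal, with an odds ratio per SD of 1.0, 1.5, 2.0 or 2.7 (log odds ratio 0, 0.4, 0.7, 1.0). The last three correspond to an AUC of about 0.61, 0.69 and 0.75 in the placebo arm. An even split of the trial into two cohorts gives 144 / 2 = 72 per arm.

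**Step 1: the plan's own figure.** With pooled variance and no continuity correction,

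n = [z(1−α/2)·√(2p̄(1−p̄)) + z(1−β)·√(p₁(1−p₁) + p₂(1−p₂))]² / (p₁−p₂)²

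where p₁ = 0.23, p₂ = 0.08, p̄ = 0.155, z(0.9875) = 2.2414 and z(0.80) = 0.8416.

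- √(2 × 0.155 × 0.845) = 0.5118
- √(0.1771 + 0.0736) = 0.5007
- n = (2.2414 × 0.5118 + 0.8416 × 0.5007)² / 0.15² = 1.5686² / 0.0225 = 109.4, so 110 per arm

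Power is Φ[(0.15√n − 2.2414 × 0.5118) / 0.5007]. This gives 80.3% at 110, 90.4% at 144 and 59.9% at 72. The stated 110 reproduces with no covariate.

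**Step 2: adding one covariate.** Three-arm trials were simulated with marginal quit rates held at 8%, 23% and 30%, 10,000 replicates per cell. The test was the Wald test at two-sided 0.025 from a logistic model with treatment and EMA, fitted without and then with the covariate. Results for 0.5 mg vs placebo are below; gains are paired differences taken before rounding, with standard error at most 0.35 points.

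| Per arm | OR per SD | Unadjusted | Adjusted | Gain (points) |
|---|---|---|---|---|
| 144 | 1.0 | 91.2% | 91.1% | −0.1 |
| 144 | 1.5 | 90.4% | 90.9% | 0.5 |
| 144 | 2.0 | 91.1% | 92.6% | 1.4 |
| 144 | 2.7 | 91.3% | 94.2% | 2.9 |
| 110 | 1.0 | 81.2% | 80.8% | −0.3 |
| 110 | 1.5 | 80.4% | 80.7% | 0.3 |
| 110 | 2.0 | 81.0% | 83.2% | 2.2 |
| 110 | 2.7 | 80.8% | 85.5% | 4.7 |
| 72 | 1.0 | 56.8% | 57.4% | 0.6 |
| 72 | 1.5 | 57.8% | 59.4% | 1.6 |
| 72 | 2.0 | 56.7% | 60.9% | 4.2 |
| 72 | 2.7 | 57.7% | 64.8% | 7.1 |

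For 1.0 mg vs placebo at 110 per arm (4,000 replicates), unadjusted power is already about 98%, and the largest gain is from 97.8% to 99.0%.

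**Step 3: type I error.** With 15% quitting in all arms, 110 per arm and 4,000 replicates, the adjusted rejection rate lay between 0.018 and 0.027 against a nominal 0.025.

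**Step 4: what adjustment changes.** At 110 per arm the median odds ratio for 0.5 mg vs placebo moves from about 3.5 unadjusted to 3.6, 3.8 and 4.1 for covariate odds ratios of 1.5, 2.0 and 2.7. The adjusted value is a conditional odds ratio, so the rise does not mean a larger effect. Expected placebo quitters are 0.08 × 110 = 8.8, 0.08 × 144 = 11.5 and 0.08 × 72 = 5.8.

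**The case against.** The strongest reply is that nothing here is wrong. An unadjusted comparison in a randomised trial is valid, the sample size was set for one, and 110 per arm reproduces. A weak covariate gains half a point or less at 110 or 144 per arm, the 1.0 mg comparison has almost nothing to gain, and no document shows that FTCD or cigarettes per day is prognostic here. EMA is in the model to check whether the two subgroups can be combined, so comparing it with an efficiency covariate is not quite fair. Participant characteristics are already planned for secondary models. All of this stands, and it limits the point to a modest improvement. It does not remove it, because secondary models leave the primary test unchanged, and the plan's default of separate cohort analyses is where the gain is largest.

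A reader might infer three stronger things that the documents do not support.

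- That the primary analysis is underpowered or invalid without covariates. Step 1 shows that the stated power is met without them.
- That adjustment costs nothing. The odds ratio becomes conditional, the arm-level rates need a stated method, and few events limit how many covariates the model can carry.
- That adjustment would make the in-person and remote cohorts comparable. They differ in the entry test (breath CO against urine cotinine), in the blood pressure and drug-screen exclusions, and in how abstinence is verified. A covariate for dependence or cohort does not remove those differences, and a cohort term has no place in a within-cohort model.

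**Conclusion.** The point holds as a small missed efficiency. The primary model leaves out baseline dependence and smoking measures that are available in both cohorts before randomisation. The size depends wholly on the assumed strength of the covariate: several points of power require an odds ratio per SD of about 2 or more, and a covariate with no prognostic value gains essentially nothing. The figures for separate cohort analyses also assume an even split, which the documents do not give. Priority is low: the change is worth making because the data are already collected.

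**What to change.** Before unblinding, amend the Main study paragraph of the Statistical Analysis Plan as follows.

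- Name one baseline covariate, the FTCD total score, in the primary logistic model, in both the interaction and the main-effects versions.
- State how the score is computed. The baseline procedures describe a five-item questionnaire, while the form in Appendix 7 numbers its items up to 6.
- Add a cohort term only if the cohorts are pooled.
- Obtain the quit rate and CI already promised for each arm, and the risk differences, by standardising the fitted model over the analysed participants. Name the CI method.
- Keep the unadjusted comparison as a sensitivity analysis.

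The cost is SAP wording and some programming; no new data or participants are needed. The downside is that the model odds ratio is conditional and must be labelled so beside the standardised risk difference. With about 9 to 12 placebo quitters expected, covariates should be held to one or two.
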